7.3.11 Withdrawal Due to Adverse Events (See also section on Subject Withdrawal)

Withdrawal due to AE should be distinguished from withdrawal due to insufficient response, according to the definition of AE noted earlier, and recorded on the appropriate AE CRF page.

When a subject withdraws due to an SAE, the SAE must be reported in accordance with the reporting requirements defined below.

7.3.12 Eliciting Adverse Event Information

The investigator is to report all directly observed AEs and all AEs spontaneously reported by the study subject. In addition, each study subject will be questioned about AEs.

7.3.13 Reporting Requirements

Each AE is assessed to determine if it meets the criteria for SAEs. If an SAE occurs, expedited reporting will follow local and international regulations, as appropriate.

Serious Adverse Event Reporting Requirements

If an SAE occurs, Pfizer is to be notified within 24 hours of investigator awareness of the event. In particular, if the SAE is fatal or life-threatening, notification to Pfizer must be made immediately, irrespective of the extent of available AE information.

This timeframe also applies to additional new information (follow-up) on previously forwarded SAE reports as well as to the initial and follow-up reporting of EIU and exposure during breast feeding cases. In the rare event that the

investigator does not become aware of the occurrence of an SAE immediately (e.g., if an outpatient study subject initially seeks treatment elsewhere), the investigator is to report the event within 24 hours after learning of it and document the time of his/her first awareness of the AE.

The IRB will be notified per institutional policy.

In addition, an investigator may be requested by Pfizer to obtain specific additional follow-up information in an expedited fashion. This information collected for SAEs is more detailed than that captured on the AE CRF. In general, this will include a description of the AE in sufficient detail to allow for a complete medical assessment of the case and independent determination of possible causality. Information on other possible causes of the event, such as concomitant medications and illnesses must be provided. In the case of a subject death, a summary of available autopsy findings must be submitted as soon as possible to the IRB and Pfizer or its designated representative.

Non-Serious Adverse Event Reporting Requirements

All AEs will be reported on the AE page(s) of the CRF. It should be noted that the form for collection of SAE information is not the same as the AE CRF. Where the same data are collected, the forms must be completed in a consistent manner. For example, the same AE term should be used on both forms. AE should be reported using concise medical terminology on the CRFs as well as on the form for collection of SAE information.

8 Planned Statistical Analyses

8.1 Pharmacokinetic Analysis

The PK concentration population is defined as all subjects enrolled and treated for whom at least 1 TOFA level or parameters of interest can be determined.

PK parameters of TOFA following multiple-dose oral administration will be derived from the concentration-time profiles using noncompartmental analysis. The observed predose concentration will also be used as the 12-hour concentration in these calculations, assuming steady state. Actual PK sampling times will be used in the derivation of PK parameters.

The plasma PK parameters from noncompartmental analysis (CL/F, Vz/F, AUCt, Cmax, Tmax, and $t_{1/2}$ (if data permit)) on Day 5 will be summarized descriptively by Visit/Day. Plasma concentrations will also be summarized descriptively by PK sampling time. Individual subject concentration-time data will be plotted using actual PK sampling times. Summary profiles (mean and median plots) of the concentration-time data will also be presented. Summary profiles will be presented on both linear-linear and log-linear scales.

The PK parameters such as CL/F and Vz/F may be compared with historical adult RA and JIA patients data using mixed effect modeling approach.

8.2 Safety Analyses

The safety population will be all subjects who received at least 1 dose of TOFA. No interim analyses are planned.

AE, SAEs and serious adverse events will be summarized using frequencies and under consideration of the number of study subjects affected. Further, in secondary analysis, we will use mixed model analysis to assess the relationship between side effects and (1) subject weight (2) background therapy with CS; (3) concurrent use of a nonbiological immunosuppressant, or (4) a history of lupus nephritis.

8.3 Effectiveness Analyses

Due to the small sample size, results may not show statistical significance. Statistical significance may not be reached in final data analysis. However, a trend towards improved clinical status may assist planning efforts of a larger clinical trial to assess efficacy.

The efficacy population will be all subjects who were enrolled in the study and received at least 1 dose of TOFA. No interim analyses are planned. We will perform intention-to-treat analyses, with the last observation carried forward in primary analyses; and will also perform analyses on observed data in secondary analyses. As this is an open-label study, no control group is available. Efficacy measures are listed under Section 7. Data of subjects who enter Part B before week 8 and/or Part C before week 24 will be

considered on a last-observation (LOC) carried forward basis for endpoints of Part A and B, respectively.

To assess the benefits of TOFA on skin manifestations of SLE, we will use descriptive analysis and contingency table analysis, using Chi-square and Fisher Exact test as appropriate, to determine the proportion of subjects who are partial or complete CLASI responders at weeks 4, 8 and 24 compared to baseline. To assess the effect of TOFA on skin damage, we will compare the change (increase) of CLASI damage score¹⁶ from baseline to the end of Part B and C, respectively, using paired T-tests.

To assess the steroid –sparing properties of TOFA, we will determine the proportion of study subjects who can discontinue steroids at the end of Part B and C, respectively. We will also evaluate steroid sparing properties of TOFA for SLE-CL by comparing steroid doses (absolute and weight-adjusted) at baseline with those in the end of Part B and C, using a paired T-test.

Similarly, we will assess TOFA effect of overall disease activity in SLE as measured by the numeric SLEDAI and BILAG scores, respectively. We will also perform sub-analyses and evaluate improvement or resolution of other organ-system activity (e.g. serological activity – measured by anti-dsDNA antibodies and low complement levels; joint counts) using paired T-tests and contingency table analysis, as appropriate. In a similar fashion the change of the other SLE core response variables (CRV) besides disease activity (SLEDAI, BILAG) will be assessed at each study visit.

To explore the effects of TOFA on quality of life, we will compare the SKINDEX score (appendix 4), well-being and pain assessments from baseline to the end of Part B and C, respectively.

We will also explore single cell expression patterns of skin biopsies of affected and non-affected skin with TOFA therapy; and examine changes in interferon α/γ receptor, STAT phosphorylation patterns with TOFA therapy using immunohistochemistry; we also explore mRNA expression patterns in peripheral blood upon treatment with TOFA with focus on interferon regulated genes.

We will also explore at week 4, 8, 12, 24, 52, and 76, the relationship of PD parameters: the inhibitory effect of TOFA on expression of IL-2 responsive target genes downstream of the JAK/STAT pathway, such as FOXP3, SOCS3, IL-2R α , interferon (IFN)- γ and granzyme B will be studied.

9. Data Safety Monitoring Plan

This study follows procedures for minimizing risks and ensuring the safety and confidentiality of human subjects, as established under both the Department of Health and Human Services and the Office for Human Research Protections (OHRP). The study will be conducted in accordance with the ethical principles of the Declaration of Helsinki and will be consistent with Good Clinical Practices (GCP) <http://www.fda.gov/cder/guidance/959fnl.pdf> and applicable regulatory requirements. A consent form describing all aspects of the study will be approved by the IRB. The nature of all possible treatment assignments, as well as their risks and potential benefits, will be fully explained to all participants. The study sites will take appropriate measures to ensure the confidentiality of the data and the well-being of the subjects. Medidata Rave will be used for Electronic Data Capture.

Please see Appendix 3 for a detailed Data Safety Monitoring Plan.

Considering the small size of the study and the substantial experience with tofacitinib use in humans (see IB; Appendix 3) no Data Safety Monitoring Board will be formed²³

10 Schedule of Assessments

Trial Period	Screening	Part A									Part B					Part C							
		1	2	3	4	5	6	7	8	9	10	11	12	13	14	15	16	17	18	19	20	21	
Visit		0	1*1	2	3	4	5	6	7	8	9	10	11	12	13	14	15	16	17	18	19	20	21
Trial Week																							76/EOS
Time Windows		Day -30 to Day -1	Day 1	±1 day	±2 day	±2 day	±3 day	±3 day	±5 day	±3 day													
Informed Consent		X																					
Inclusion/exclusion criteria		X	X																				
Medical history, medication		X																					
Tuberculosis assessment		X																					
Serum virology (HBsAg, HCV, HIV, VZV)		X																					
Serum pregnancy test*2		X																					
Urine pregnancy test*2			X		X						X		X		X	X	X	X	X	X	X	X	
Vital sign, weight, height*3		X	X	X	X	X	X	X	X	X	X	X	X	X	X	X	X	X	X	X	X	X	
Investigational Product Dispensing (or as needed)			X				X				X		X	X	X	X	X	X	X	X	X	X	X
Patient Dosing Diary review				X	X	X	X	X	X	X	X	X	X	X	X	X	X	X	X	X	X	X	
Complete physical examination		X	X			X					X		X	X	X	X	X	X	X	X	X	X	X
Laboratory Assessment																							
Hematology		X	X	X	X	X	X	X	X	X	X	X	X	X	X	X	X	X	X	X	X	X	
Clinical chemistry		X	X	X	X	X	X	X	X	X	X	X	X	X	X	X	X	X	X	X	X	X	
Urinalysis incl. sediment		X	X			X					X		X	X	X	X	X	X	X	X	X	X	
Urine protein: creatinine ratio		X	X			X					X		X	X	X	X	X	X	X	X	X	X	
Complement C3, C4,			X			X					X		X	X	X	X	X	X	X	X	X	X	
ANA*4 and anti-ds DNA Abs			X			X					X		X	X	X	X	X	X	X	X	X	X	
ESR			X			X					X												X
Efficacy																							
CLASI		X	X	X	X	X	X	X	X	X	X	X	X	X	X	X	X	X	X	X	X	X	
Photography (selected)			X							X													
SLICC/ACR damage index			X								X												X
SLEDAI-2K, MD Global Assessments, BILAG			X			X					X		X	X	X	X	X	X	X	X	X	X	
Patient's Global Assessment, Skindex			X			X					X		X	X	X	X	X	X	X	X	X	X	
Pharmacokinetic																							
Plasma TOFA-Part A (Cohort 1) *5			X*6																				
Pharmacodynamic																							
**Gene expression profiling of IL2 mediated genes in whole blood					X						X						X						
**Phosphospecific flow cytometry of blood T-cells & other relevant cells					X						X						X						
**SC-RNA SEQ in skin biopsies (selected)				X														X					
**Skin biopsy (selected) *7			X														X *7						
Safety																							
Adverse events/SAE		X	X	X	X	X	X	X	X	X	X	X	X	X	X	X	X	X	X	X	X	X	
Concomitant medications		X	X	X	X	X	X	X	X	X	X	X	X	X	X	X	X	X	X	X	X	X	
TT, diphtheria, varicella, influenza titer; EBV and CMV PCR		X															X						

¹*Part A - Day 5 after TD1

²Females only

³Height only at screening

⁴ANA only at baseline on TD1

⁵ A total of 24.5 mL of blood will be taken at these visits for pharmacodynamics tests

⁶PK samples will be drawn on Day 5 of Trial Week 1. re - morning dose for Day 5 and at 0.5, 1, 2, 4 and 8 hours post morning dose.

⁷ Two 3mm punch biopsies will be collected. 1st punch collected during week one. 2nd punch collected between weeks 8-15.

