Cohort 2 subjects will be seen in weekly intervals during Part A.

Cohort 1 and 2 subjects with clinical remission of SLE-CL can enter Part B as early as week 4 post baseline. Subjects who move from Part A to Part B prior to Week 8, will still be evaluated using the same visit schedule as subjects remaining in Part A until week 8.

Part B (week 8* – 24)

The primary objective of Part B is to assess safety and tolerability of TOFA, secondary objectives include effectiveness. Specifically, the PK of TOFA at the 5 mg dose based on Cohort 1 will be characterized.

- If CS are primarily given for SLE-CL, then CS may be decreased for clinically significant improvement as defined by a *Cutaneous Lupus Erythematosus Disease Area and Severity Index (CLASI)* activity score by $\geq 50\%$ from baseline and must be tapered for CLASI activity scores of 0 for > 2 months.

* Roll-over subjects in SLE-CL clinical remission may enter Part B as early as week 4

- If CS are mainly prescribed for other SLE manifestations besides SLE-CL, then CS can be decreased as per the investigator's decision, based on clinically significant findings of improvement.
- If the subject has been discontinued from CS and continues to be in SLE-CL clinical remission (CLASI activity score = 0), then the subject can enter Part C.

Subjects who move from Parts B to Part C prior to Week 24 will still be seen using the same visit schedule as subjects remaining in Part B until week 24.

Part C (week 24[†] – 76)

During Part C all therapies can be altered, per investigator discretion, with the exception of TOFA. The TOFA dose will remain stable throughout the study. Subjects who exit Part A or B early due to SLE-CL improvement will remain in Part C until they have been in the study for a total of 76 weeks.

4. Study description

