4.1 Primary Objective(s) & Endpoint(s)

Primary objective

Part A (Cohort 1 only):

- To evaluate the pharmacokinetic (PK) profiles of TOFA in young adults with SLE-CL who are on stable treatment for SLE

Part A (Cohort 1 and Cohort 2):

- To evaluate the safety and tolerability of TOFA in young adults with SLE-CL

Part B and C:

- To evaluate the safety and tolerability of TOFA in young adults with SLE-CL

Primary endpoints

Part A (Cohort 1 only):

- Day 5: AUC_{inf} and C_{max} of tofacitinib

Part B: At Week 24:

- Nature, severity, and frequency of adverse events
- Incidence and severity of laboratory abnormalities

[†] as early as week 8 for subjects with clinical remission of SLE -CL and off CS

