4.2 Key Secondary Objective(s) & Endpoint(s)

Secondary objectives

- To evaluate the efficacy of TOFA with SLE-CL over time compared to baseline

Secondary endpoint

Part A and B:

- Proportion of subjects that achieve a skin response (complete or partial response) as per the validated (CLASI) at weeks 4, 8 and 24 compared to baseline at TD1¹⁴. Response is defined as follows:
 - *Complete response (CR)* : complete resolution of the inflammatory rash (CLASI activity score = 0);
 - *Partial response (PR)*: $\geq 20\%$ improvement of the CLASI activity score. A partial response (PR) is considered clinically significant
 - *No response*: $< 20\%$ improvement or even worsening of the CLASI activity score
 - *Cutaneous relapse*: a new CLASI activity score ≥ 4 in those subjects who previously achieved CR of SLE-CL (CLASI=0)

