4.3 Exploratory Objective(s) & Endpoint(s)

Exploratory objectives

Part A:

- To evaluate single cell expression patterns of skin biopsies of affected and non-affected skin with TOFA therapy
- To examine changes in interferon α/γ receptor, STAT phosphorylation patterns with TOFA therapy using immunohistochemistry
- To investigate mRNA expression patterns in peripheral blood upon treatment with TOFA with focus on interferon regulated genes

Parts B and C:

- To evaluate steroid sparing properties of TOFA for SLE-CL
- To evaluate TOFA effect of overall disease activity in SLE as measured by the SLEDAI and BILAG
- To evaluate effects of TOFA on quality of life as measured by the Skindex (appendix 4) and overall well-being

Exploratory endpoints at week 4, 8, 12, 24, 52, and 76

Part A: Pharmacodynamics (PD)

- PD parameters include assessment of inhibitory effect of TOFA on expression of IL-2 responsive target genes downstream of the JAK/STAT pathway, such as FOXP3, SOCS3, IL-2R α , interferon - γ and granzyme B.

Parts B and C:

- Decrease of absolute dose of systemic CS from baseline
- Decrease of body weight adjusted CS dose from baseline
 - CS dosing is measured in prednisone-equivalents
- Proportion of subjects who discontinue systemic CS
- Proportion of subjects with cutaneous relapse
- Change of BILAG score from baseline¹³
- Absolute value and percent change in plasma: Complement C3 and C4d, autoantibodies (anti-dsDNA)
- Change in number of inflamed joints from baseline¹⁴
- Change in SKINDEX score from baseline¹⁵
- Change of CLASI damage score¹⁶ from baseline
- Change in SLEDAI score at each time point
- Change in protein: creatinine ratio at each time point.
- Change in subject's overall well-being at each time point
- Change in subject's ESR
- Proportion of subjects with clinically important reduction in SLE activity at each time point, based on CRV changes compared to baseline
- Proportion of subjects with flare of SLE activity at each time point, as defined by the BILAG¹⁷

Data of subjects who enter Part B before week 8 and/or Part C before week 24 will be considered on a last-observation (LOC) carried forward basis for endpoints of Part A and B, respectively.

5. Study Participants

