This is a 3-part study designed to evaluate the Pharmacokinetics and Pharmacodynamics of TOFA in young adults with active SLE-CL (CLASI activity score>8) aged 18 to 45 years. Safety and efficacy will be evaluated as secondary objectives. Subjects achieving CR of SLE-CL may be permitted to roll-over to subsequent parts of the study earlier.

In Part A (baseline – week 8), subjects will be enrolled in an open-label arm to receive TOFA orally twice per day. PK analysis will be performed on Cohort 1 only to measure PK parameters. Starting week 4, subjects may roll over from Part A to Part B early, if there is clinical remission of SLE-CL (CLASI activity score = 0).

In Part B (week 8 – 24), subjects will continue TOFA as in Part A but CS can be decreased for clinically significant improvement of SLE-CL by $\geq 50\%$ from baseline. Subjects who maintain clinical remission of SLE-CL and succeeded in discontinuing CS, can roll over to Part C prior to week 24.

In Part C (week 24 – 76), subjects off CS who are in clinical remission of SLE-CL will be able to taper and change other background medications. TOFA dosage will remain stable.

It is planned to enroll:

Cohorts 1: n=10, weight > 40 kg age ≥ 18 up to and including 45 years.

Cohort 2: n=10; weight > 40 kg and age \geq 18 years up to and including 45 years. Enrollment of subjects into Cohort 2 will commence once enrollment of Cohort 1 are completed.

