 4. ESR
- Proportion of subjects with clinically important reduction in SLE activity at each time point, based on CRV changes compared to baseline
- Proportion of subjects with flare of SLE activity at each time point, based on CRV changes compared to baseline

Data of subjects who enter Part B before week 8 and/or Part C before week 24 will be considered on a last-observation (LOC) carried forward basis for endpoints of Part A and B, respectively.

C. INCLUSION/EXCLUSION CRITERIA

INCLUSION CRITERIA

1. Male or female age 18 to 45 years and >40 kg body weight.
2. Fulfills at least 4 out of the 11 Classification Criteria for SLE by the time of screening.
3. Written informed consent, given before any trial-related procedure. Subjects or their legal representative must have read and understood the informed consent form, must fully understand the requirements of the trial, and must be willing to comply with all trial visits and assessments.
4. CLASI activity score of 8 or higher at screening and baseline despite standard therapy.
5. Stable dose of prednisone of ≤ 20 mg/day within 2 weeks of enrollment.
6. Female subjects of childbearing potential must use a highly effective method of contraception to prevent pregnancy (abstinence is considered highly effective) and must agree to continue

to practice adequate contraception for the duration of their participation in the trial and for 28 days following the last dose of TOFA.

7. Female subjects of childbearing potential must have a negative serum pregnancy test at screening and a negative urine pregnancy test at Trial Day 1 before dosing.
8. For subjects receiving leflunomide treatment, total daily dose does not exceed 20 mg.
9. A negative QuantiFERON-TB Gold In-Tube test performed within the 3 months prior to screening. A negative PPD test can be substituted for the QuantiFERON-TB.
10. Patients either have protective varicella titers or evidence of having been vaccinated against varicella.

EXCLUSION CRITERIA

Subjects are not eligible for this trial if they fulfill any of the following exclusion criteria:

1. Mild SLE -CL defined as a CLASI activity score of 7 or lower at screening and baseline
2. Increase in CS dosing within 2 weeks prior to Trial Day 1, or expected to require an increase in CS dosing during the first 4 weeks of the study.
3. Use of i.v. corticosteroids within 4 weeks prior to Trial Day 1.

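### Carry-forward for early roll-over subjects is not limited to missing visits, and primary LOCF counts a skin responder later stopped as a treatment failure as a week-24 responder

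*Combined protocol and SAP*

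**What the plan says.** **Primary rule.** Section 8.3 takes all treated subjects and states: "We will perform intention-to-treat analyses, with the last observation carried forward in primary analyses; and will also perform analyses on observed data", the latter as secondary.

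**Roll-over rule.** Sections 4.3 and 8.3 and Appendix 3 B each add that the data of subjects entering Part B before week 8, or Part C before week 24, are to be "considered on a last-observation (LOC) carried forward basis for endpoints of Part A and B, respectively". None of the three mentions a missing visit.

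**Who rolls over early.** Entry to Part B is possible from week 4 with a CLASI activity score of 0 (sections 3 and 6). Entry to Part C is possible "as early as week 8 for subjects with clinical remission of SLE -CL and off CS" (footnote to 4.1).

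**Their visits.** Section 3 says: "Subjects who move from Part A to Part B prior to Week 8, will still be evaluated using the same visit schedule" as those still in Part A. It says the same for early Part C entrants up to week 24. The schedule in section 10 marks CLASI at each visit.

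**Endpoints.** The secondary endpoint in 4.2 is the "Proportion of subjects that achieve a skin response (complete or partial response) as per the validated (CLASI) at weeks 4, 8 and 24". Partial response is at least 20% improvement. Section 8.3 also plans to "determine the proportion of study subjects who can discontinue steroids at the end of Part B and C, respectively".

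**Failures.** Section 6.5 lists events that make a subject a treatment failure and end participation. Section 6.2 adds steroids not brought back to baseline within 14 days, and 7.3.4 requires discontinuation for serious infection. Neither 4.2 nor 8.3 says how such a subject enters the responder count. After stopping, 7.1 sets a phone call at 10 weeks, and 6.5 asks for a final visit where applicable.

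**The concern.** There are two separate problems.

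(a) The general LOCF rule already deals with missing visits. The roll-over sentence is triggered by early entry to the next Part. Its literal effect is to put the value at roll-over in place of one recorded later. For CLASI that value is 0, the lowest possible score, so the substitution can only favour the drug. Early Part C entrants are also off steroids, so that status is frozen too.

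(b) Response is defined on CLASI alone, and nothing in 8.3 deals with treatment failure. A subject can therefore be a failure under 6.5 and a responder in the primary week-24 analysis.

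Section 8.3 offers these results as help in planning a larger efficacy trial. Both rules push the estimates upward, and no planned table shows how many subjects are involved.

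**Working it through.** The plan gives no expected response rate, dropout rate or formal sample size, so there is no figure to reproduce. The documents supply N = 20, minimum baseline CLASI 8, the 20% threshold, the relapse score of 4, and up to 80% of subjects on steroids. All subject counts below are assumptions. One subject is 1/20 = 5 points.

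**(a) Gap bridged.** Part B entry from week 4, endpoint at week 8: up to 8 − 4 = 4 weeks. Part C entry from week 8, endpoint at week 24: up to 24 − 8 = 16 weeks.

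**(a) Combined response.** With baseline b and later score s, response is lost only if (b − s)/b < 0.20, that is s > 0.8b. The lowest such whole scores are 7 from b = 8 (12.5% improvement), 9 from 10 (10%), 13 from 15 (13.3%) and 17 from 20 (15%). A relapse to 4 from 8 is (8 − 4)/8 = 50% improvement and still a partial response. The usual change in the CR-or-PR rate is therefore zero.

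**(a) Complete response.** Assume 4 early roll-over subjects are the only complete responders and k of them are no longer at 0 at the endpoint week. Carried: 4/20 = 20% for every k. Recorded: (4 − k)/20 = 20%, 15%, 10% for k = 0, 1, 2.

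**(a) Steroid discontinuation at the end of Part B.** Take 0.80 × 20 = 16 steroid users. Assume 4 enter Part C early off steroids, no one else stops, and k are back on steroids at week 24. Carried: 4/16 = 25%. Recorded: (4 − k)/16 = 25%, 18.75%, 12.5%.

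**(b) Failure after response.** Assume 8 responders among completers and f responders later stopped as failures. The last column also assumes 4 non-responders stopped at week 8.

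| f | LOCF (8+f)/20 | Failure as non-response 8/20 | Observed 8/(20−f) | Observed 8/(16−f) |
|---|---|---|---|---|
| 0 | 40% | 40% | 40% | 50% |
| 1 | 45% | 40% | 42.1% | 53.3% |
| 2 | 50% | 40% | 44.4% | 57.1% |
| 3 | 55% | 40% | 47.1% | 61.5% |

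The observed-data analysis removes the failure from numerator and denominator. Once week-8 exits are also dropped, it lies above LOCF, so it is no check on (b).

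**(b) Other exits.** Take f = 2 and w = 0, 1, 2 further responders who leave for other reasons. LOCF: (10 + w)/20 = 50%, 55%, 60%. Failures only as non-response: (8 + w)/20 = 40%, 45%, 50%. All exits as non-response: 8/20 = 40%. The classing of other exits matters as much as that of failures.

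**Scale.** Exact (Clopper-Pearson) 95% intervals: 8/20, 19.1% to 63.9%; 10/20, 27.2% to 72.8%.

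**The case against.** On (a), the plan never says that recorded scores are set aside. The document repeats itself elsewhere, so a redundant sentence is weak evidence of intent, and keeping roll-over subjects on the same visits fits an intention to use their scores. Freezing the value at roll-over also has a rationale: background therapy may change afterwards, and the frozen value reflects response before that. Both points stand. They make this an ambiguity with a literal reading that favours the drug, and they justify keeping the roll-over value as a sensitivity result. They do not justify leaving the sentence open to two different tables. The observed-data analysis would check (a) if it uses the recorded scores, but 8.3 does not say so.

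A reader might infer that the roll-over rule inflates the planned skin response rate. The threshold arithmetic does not support that. The effect is on the complete-response category, which 4.2 defines but does not make a stand-alone endpoint, and on exploratory relapse and steroid outcomes. A relapse after early Part C entry can still be counted under Part C. Early Part B entrants need only CLASI 0, and 6.2 holds steroids stable through week 4, so freezing their steroid dose gives no comparable advantage.

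On (b), a reader might infer that LOCF miscounts every treatment failure. It does not. A subject stopped at week 8 for no CLASI improvement is carried as a non-responder. The background-therapy criterion in 6.5 is for non-renal SLE, which can include skin; the last CLASI may then already show the worsening.

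Nor are failures hidden from the report: adverse events, laboratory abnormalities, flares and steroid doses are all endpoints. What is missing is their cross-classification with skin response. Finally, counting a low blood count or an infection as skin non-response is one choice of estimand among several. The documents do not show that it must be the main analysis.

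**Conclusion.** Both parts hold in limited form.

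(a) The roll-over sentence is not restricted to missing visits. On its literal reading it can overstate complete response and end-of-Part-B steroid discontinuation and hide relapse at Part A and B time points, over up to 4 or 16 weeks. The illustrations give differences of 0 to 10 points for complete response and 0 to 12.5 points for steroid discontinuation, on assumed counts. The CR-or-PR rate normally does not change. The documents do not support the stronger claim that recorded data will certainly be discarded.

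(b) A responder stopped before week 24 as a treatment failure or for serious infection is a primary-analysis responder, mainly where the ground is not skin. No planned analysis shows otherwise. Each such subject adds 5 points; two add 10. That is well inside the sampling error at N = 20, but it runs in one direction and would not shrink with more subjects.

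Severity is minor to moderate: these are secondary and exploratory endpoints in an open-label, single-arm study whose primary aims are PK and safety.

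**What to change.** **Roll-over sentence (4.3, 8.3 and Appendix 3 B).** State that, for every Part A and B endpoint, the value recorded at the scheduled week is used whatever Part the subject is in, with carry-forward only if that assessment is missing. Flag early roll-over subjects in the tables. Keep the value at roll-over as a labelled sensitivity result, since recorded values include the effect of permitted background changes.

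**Responder analysis (8.3).** Next to the LOCF result, pre-specify an analysis of all treated subjects in which treatment failure under 6.5 or 6.2, or a serious-infection stop under 7.3.4, before the time point is non-response. In that analysis keep other exits (withdrawal, a stop under 6.4, and pregnancy, although it is on the 6.5 list) at the last observed value. Show them as non-response in a second line. Report the number of subjects reclassified.

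**Cost.** Wording and a few table lines; no new visits or data. The reported rate may be somewhat lower. The composite mixes skin response with non-skin failure and should be labelled so; safety events are still reported separately.
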